3.3.2 Definition and Management of Dose-limiting Toxicity

A DLT is defined as a toxicity of CTC grade 3 or greater severity (based on CTCAE Version 3.0) that is deemed by the Investigator related to the investigational agent, occurs within 4 weeks of administration, and is confirmed by the Investigator and Sponsor, or by the DSMB. A toxicity of CTC grade 2 that is deemed by the Investigator related to the investigational agent and occurs within 4 weeks of administration may also be reported as a potential DLT if the Investigator considers it a clinically significant safety concern.

Given the long list of expected toxicities experienced by patients undergoing HSCT, careful determination of attribution will be particularly important (see Section 5.2).

Sites must notify the Sponsor within 24 hours of having knowledge of a potential DLT. In cases where it is not clear whether an event should be considered related, the Investigator should discuss the case with the Sponsor's medical monitor. Within 24 hours of notification of a potential DLT, the Sponsor will contact the Investigator to discuss the event and together will confirm if it is a DLT. If it is determined that an AE meets all of the criteria for DLT, the subject will discontinue study drug. After receiving treatment for the toxicity (if necessary), the subject will be closely monitored until the toxicity is resolved to no worse than grade 2 severity (grade 1 if reported toxicity is initially grade 2) or is stabilized, at which point he/she will be removed from the study.

If the Investigator and Sponsor cannot agree on the determination of a DLT, the issue will be escalated to the DSMB and the subject will discontinue study drug. Within 7 days of the Sponsor receiving notification of a potential DLT, the DSMB must convene (most likely by teleconference) to determine whether the event is to be classified as a DLT. After receiving treatment for the toxicity (if necessary), the subject will be closely monitored until the

toxicity is resolved to no worse than grade 2 severity (grade 1 if reported toxicity is initially grade 2) or is stabilized, at which point he/she will be removed from the study.

The Sponsor will provide written notification of all DLT determination decisions to the Investigator and DSMB members.

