3.3.3 Definition of Maximum Tolerated Dose

The MTD is defined as the highest dose at which at least six subjects complete the treatment course with no more than one subject experiencing a DLT. If two or more subjects experience a DLT at a given dose level, the MTD will have been exceeded and no additional subjects will be treated at that level. The DSMB will convene to examine the data and review the drug-relatedness of the relevant toxicities in light of the typically complex course and safety experience of HSCT patients. If the DSMB agrees that the relevant toxicities were drug-related and met the other criteria for DLT, no further dose escalation will occur and, depending on the nature of the DLTs, the study may be stopped. Throughout the study, the Sponsor will report any significant findings by the DSMB to the FDA.

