3.5 Enrollment

Once prescreening is completed and subject eligibility is confirmed, a subject will be assigned a subject number by the Sponsor. Donors who sign an informed consent will be assigned a tracking number that can be used for tracking donor samples and will link those samples with the subject who received the donor's stem cells.

Sites must contact the following individual for subject number assignment:

[name] [contact]

[contact]

Eligible subjects will be assigned to one of five successive dose groups of six subjects each (see Section 3.1 and Table 1). Enrolled subjects who discontinue the trial prior to receiving opebacan will be replaced. Subjects will also be replaced if they do not receive at least 80% of their scheduled dose of opebacan and/or do not complete assessments for at least 7 days following the end of their opebacan infusion.

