4.5 Discontinuation

4.5.1 Subject Discontinuation

Subjects may withdraw or be withdrawn from the study at any time. Every effort should be made to obtain complete follow-up information on subjects who receive any amount of opebacan and discontinue from the study prematurely. The reason(s) for a subject's discontinuation from the study must be clearly documented in the subject's medical records and on the CRF

A subject who experiences DLT at any dose level will discontinue study drug. After receiving treatment for the toxicity (if necessary), the subject will be closely monitored until the toxicity is resolved to no worse than grade 2 (grade 1 if reported toxicity is initially grade 2) severity or is stabilized, at which point he/she will be removed from the study.

In the event that a subject discontinues participation in the study prior to receiving opebacan, the subject will be replaced. No follow-up or additional procedures will be performed on subjects discontinuing prior to receiving opebacan.

Subjects will also be replaced if they do not receive at least 80% of their scheduled dose of opebacan and/or do not complete assessments for at least 7 days following the end of their opebacan infusion.

If the subject discontinues participation in the study after receiving any amount of opebacan, every effort should be made to complete as many subsequent protocol evaluations as possible.

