5.5 Type and Duration of Follow-up After Adverse Events

5.5.1 Post Treatment Follow-up

All subjects receiving any amount of drug will be followed until Day 100. All protocoldefined AEs occurring during the treatment and post-treatment periods should be fully evaluated by the Investigator, recorded on the appropriate pages of the CRF, and documented in the subjects' files.

SAEs that occur after the subject has completed the clinical trial generally need not to be reported unless the Investigator believes the event may be related to the administration of study drug.

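### A subject with a DLT is taken off study although every dosed subject is to be followed to Day 100, and neither the replacement rule nor Table 2 says how such a subject is handled

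*Supplement*

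**What the plan says.** **Removal.** Under Section 3.3.2 a confirmed DLT ends study drug. The subject is then monitored until the toxicity has improved to a set grade "or is stabilized, at which point he/she will be removed from the study". The same sentence is repeated for events on which the investigator and sponsor disagree and which go to the DSMB; there it does not depend on what the DSMB decides. Section 4.5.1 says it again: "A subject who experiences DLT at any dose level will discontinue study drug", followed by monitoring and removal.

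**Follow-up.** Section 5.5.1 states: "All subjects receiving any amount of drug will be followed until Day 100". For anyone who stops after receiving opebacan, Section 4.5.1 asks that "every effort should be made to complete as many subsequent protocol evaluations as possible". Sections 3.1 and 3.3.4 place the DSMB review after all subjects in a group have finished procedures through Day 28.

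**Replacement.** Section 3.5 reads: "Subjects will also be replaced if they do not receive at least 80% of their scheduled dose of opebacan and/or do not complete assessments", the assessments being those of at least 7 days after the infusion ends. Section 4.5.1 repeats the rule. Neither section mentions DLTs.

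**Counting.** Sections 3.1 and 3.3.4 allow escalation with at most one DLT subject in the group. Section 3.3.3 defines the MTD as the "highest dose at which at least six subjects complete the treatment course with no more than one subject experiencing a DLT". Its next sentence says that with two or more DLT subjects the MTD has been exceeded and nobody further is treated at that level; Section 6.5.2 also treats two as exceeding the MTD. Table 2 gives binomial escalation probabilities for exactly six subjects.

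**The concern.** There are two separate problems.

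First, the instruction specific to DLTs conflicts with the general follow-up rule. A site cannot both remove the subject and follow that subject to Day 100, and the specific instruction is the one more likely to be applied. Any data lost would be lost selectively, in subjects judged to have been harmed by the drug. Section 3.2.1.4 identifies cardiac toxicity as the nonclinical signal and suggests that duration of exposure matters, so later LVEF and cardiac serology in these subjects are informative.

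Second, the replacement rule depends on dose received and assessments completed, and a DLT can affect both. A cohort with a DLT can therefore grow beyond six, while the stated operating characteristics assume that it does not. The plan is silent on the subject's place in the denominator in the one situation where the escalation decision is sensitive to it.

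**Working it through.** **1. What removal can cost.** According to Section 4.3.2 and Appendix 1:

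- The only post-dose antibody sample is at Day 28.
- LVEF and aGvHD grading fall at Days 7, 14, 21, 28 and 100, with further aGvHD grading at Day 42 for subjects still in hospital and, if possible, at Days 56, 70 and 84.
- Cardiac serology continues to Day 28, and to Day 49 for subjects still in hospital.
- The discharge or early-termination visit covers adverse events, concomitant medication, metabolic assessment, physical examination and vital signs. It includes none of LVEF, cardiac serology, antibody or aGvHD grading.

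A subject removed before Day 28 would thus have no post-dose antibody result and no later cardiac or aGvHD data. Such a subject also cannot finish Day 28 procedures. Read literally, either the DSMB trigger is not met or that subject no longer belongs to the group; the plan does not say which.

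**2. When a DLT leads to replacement.** Table 1 gives totals of 22, 31, 40, 88 and 172 mg/kg: a 4 mg/kg infusion over 30 minutes plus a daily rate *r*. The time to 80% of dose is (0.8 × total − 4)/*r* + 0.5/24 days.

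- Group 1: (17.6 − 4)/6 + 0.02 = 2.29 days of 3. Groups 2 and 3: 2.33 and 2.35 days.
- Group 4: (70.4 − 4)/12 + 0.02 = 5.55 days of 7.
- Group 5: (137.6 − 4)/12 + 0.02 = 11.15 days of 14.

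A DLT stopping the infusion before these times meets the replacement rule. Section 5.1 puts acute infusional events at 12 to 48 hours, before 2.29 days (55 hours), so such a DLT is plausible in any group. The first MTD condition points the same way: one DLT stop among six leaves five completers, so a seventh subject is needed to reach six.

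How often this happens depends on DLT timing, which the documents do not give. The window is only "occurs within 4 weeks of administration", without saying whether it runs from the start or the end of the infusion. Assuming uniform onset, and taking both readings of the window, the share of DLTs falling before the 80% point is:

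- Groups 1–3: 7–8% (for example 2.29/31 to 2.35/28).
- Group 4: 16–20% (5.55/35 to 5.55/28).
- Group 5: 27–40% (11.15/42 to 11.15/28).

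If every DLT up to 7 days after the planned end of infusion also led to missed assessments, the upper bounds would be 32–36%, 40–50% and 50–75%.

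**3. Effect on Table 2.** For a fixed six, P(escalate) = (1−p)^6 + 6p(1−p)^5. At p = .30 this is .1176 + .3025 = .4202; at p = .20 it is .2621 + .3932 = .6554. All eight Table 2 entries reproduce to four decimals.

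Now let a share *f* of DLT subjects be replaced, with every DLT still counted. Escalation needs no DLT in six, or one DLT that is either not replaced or replaced by a subject without a DLT:

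P = (1−p)^6 + 6p[f(1−p)^6 + (1−f)(1−p)^5].

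With f = 1 this becomes (1−p)^6(1+6p). At p = .30: .1176 × 2.8 = .3294. At p = .20: .2621 × 2.2 = .5767.

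| DLT rate | Table 2 (f = 0) | f = 50% | f = 100% |
|---|---|---|---|
| 10% | .886 | .868 | .850 |
| 20% | .655 | .616 | .577 |
| 30% | .420 | .375 | .329 |
| 40% | .233 | .196 | .159 |

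The values of *f* are assumptions. Replacement for other reasons is left out.

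**The case against.** The best defence is that the protocol protects the safety decision elsewhere, and much of that defence stands.

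A reader might infer that a replaced subject's DLT leaves the count, so that a level could be refilled until six clean completers remain. The documents do not support this. Section 3.3.3 stops treatment at a level after two DLTs, so no such refilling can occur. Its MTD definition has two conditions, and a subject who did not complete still counts under the second. Sections 3.1, 3.3.4 and 6.5.2 count any subject in the group with a DLT. Section 6.0 keeps all treated subjects in the safety analyses, and Section 3.3.2 requires investigators, sponsor and DSMB to agree before escalation. On the reading the text favours, replacement makes escalation less likely, which is the cautious direction.

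A reader might also infer that most DLT subjects would be replaced. Under uniform onset, even the upper bounds exceed one half only in Group 5, after which there is no further escalation. Clustering of DLTs during the infusion would raise the share, but the documents give no basis for assuming it.

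Finally, loss of data is not settled. Sections 4.5.1 and 5.5.1 ask for follow-up, and removal waits for resolution or stabilisation. That leaves a contradiction rather than a rule, but the contradiction is real. The early-termination visit does not fill the gap, because it omits the cardiac, antibody and aGvHD assessments.

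**Conclusion.** The point holds as a conflict between passages and a gap in the counting rules. The removal wording in Sections 3.3.2 and 4.5.1 cannot be squared with Day 100 follow-up in Section 5.5.1, with Section 4.5.1's own request for complete follow-up, or with the Day 28 trigger in Sections 3.1 and 3.3.4. Applied as written, it can end scheduled safety data in subjects who had a DLT.

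On counting, the DLT remains in the numerator. The defect is that a replaced DLT subject enlarges the cohort and Table 2 then overstates the chance of escalating. The overstatement is at most .420 against .329 at a 30% rate (.091) and .655 against .577 at 20% (.079), both on the assumption that every DLT subject is replaced. With fewer replaced it is smaller, for example .375 at a 30% rate when half are. The escalation rule itself is not undermined. This is a correction worth making, of moderate weight, and not a flaw that invalidates the design.

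**What to change.** 1. Reconcile Sections 3.3.2 and 4.5.1 with Section 5.5.1 so that a DLT subject, off study drug, stays in the already scheduled follow-up to Day 100. The rules for stopping drug and managing the toxicity need not change.
2. In Sections 3.5 and 4.5.1, state that a dosed subject with a DLT always counts in both numerator and denominator for the escalation and MTD decisions, and that any replacement is an additional subject, for PK.
3. Add a note to Table 2 that it assumes a fixed six without replacement, or restate it with the replacement case alongside.

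The cost is protocol wording, one table note, and the remaining visits, already in the schedule, for the few subjects with a DLT.

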Dose escalation must be delayed until a confirmed DLT has resolved or stabilized at grade 2 (grade 1 if reported toxicity is initially grade 2) or less. All Investigators in the study will be notified of all reported toxicities at each dose level before escalation. The Investigators, Sponsor, and DSMB must agree that proceeding with dose/duration escalation is appropriate before the first subject can be treated in the next study group.

The DSMB will be an independent, interdisciplinary body with four members, including two oncologists, one additional specialist (possibly a cardiologist), and XOMA's biostatistician. The DSMB collectively will have substantial experience in the treatment of subjects undergoing HSCT and in the conduct and monitoring of randomized clinical trials. A full description of the DSMB's responsibilities and procedures will be provided in the DSMB Charter under separate cover.

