3.3.4 Dose Escalation Plan

Subjects will be enrolled sequentially according to the dose escalation diagram shown in Figure 4. If a DLT occurs in any subject, it must be treated, if necessary, and monitored until it stabilizes or recovers to no worse than CTC grade 2 toxicity (grade 1 if reported toxicity is initially grade 2) prior to additional enrollment. Subjects will be monitored for toxicity with assessments listed in Appendix 1 (Schedule of Assessments).

To minimize the chance of simultaneous graft failures possibly due to exposure to opebacan, only two subjects may be simultaneously enrolled in any dose group until one of them successfully engrafts, defined as ANC $\geq 500/\mu L$ for three consecutive days, with the first day (the day of engraftment) occurring no later than Day 28. Once engraftment occurs in one of the first two subjects in a dose group, the third subject may be enrolled. When engraftment occurs in a second subject within a dose group, the fourth subject may be enrolled, and when

engraftment occurs in a third subject in a dose group, the fifth subject may be enrolled. Finally, when engraftment occurs in a fourth subject in a dose group, the sixth subject may be enrolled.

After all subjects in a dose group have completed study procedures through Day 28, all available safety information will be reviewed by the DSMB. Dosing may begin for the next dose group at the next higher dose level if no more than one subject in the previous group has experienced a DLT and, in the opinion of the DSMB, there are no clinically significant safety concerns at the previous dose level. If, in the opinion of the DSMB, there are clinically significant safety concerns, the DSMB may recommend that the study be discontinued.

If graft failure occurs in any dose group, that dose group will be expanded to 12 subjects. If a second graft failure occurs in the expanded cohort, the DSMB will determine if the study should be stopped after looking at the data for the two subjects whose grafts failed. As with other dose groups, enrollment in the expanded cohort will be staggered to minimize the chance of multiple graft failures. Only two subjects may be simultaneously enrolled until one of them successfully engrafts, at which time an additional subject may be enrolled.

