4.5.2 Study Discontinuation

XOMA has the right to terminate this study at any time for any reason. Reasons for terminating the study may include the following:

- The incidence or severity of AEs indicates a potential health hazard to subjects.
- Subject enrollment is unsatisfactory.

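### The board described as independent includes the sponsor's biostatistician, yet it rules on DLT disputes to which the sponsor is a party and re-reviews drug-relatedness before the MTD is settled

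*Supplement*

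**What the plan says.** On the make-up of the board, section 3.3.2 states: "The DSMB will be an independent, interdisciplinary body with four members". The sentence goes on to list them, "including two oncologists, one additional specialist (possibly a cardiologist), and XOMA's biostatistician". The company named there is the sponsor. Section 4.5.2 says "XOMA has the right to terminate this study at any time for any reason", and the medical monitor whom 3.3.2 calls the sponsor's is called the company's own in 3.6.5.2.

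On the board's tasks:

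- **Disputed DLTs (3.3.2).** "If the Investigator and Sponsor cannot agree on the determination of a DLT, the issue will be escalated to the DSMB". Within 7 days of the sponsor being notified, "the DSMB must convene (most likely by teleconference) to determine whether the event is to be classified as a DLT".
- **Two or more DLTs (3.3.3).** The board convenes and reviews whether the toxicities were drug-related. "If the DSMB agrees that the relevant toxicities were drug-related and met the other criteria for DLT, no further dose escalation will occur".
- **Escalation (3.3.4).** At most one subject with a DLT is allowed (the quotation stops just before the DLT is named): "Dosing may begin for the next dose group at the next higher dose level if no more than one subject in the previous group has". The board must also see no clinically significant safety concern.

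Section 3.3.2 also requires the investigators, the sponsor and the board all to agree before the next group starts. It leaves the board's detailed procedures to a separate Charter.

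**The concern.** The DLT count is the numerical criterion for escalation and defines the MTD. The trial is open-label, and 3.3.2 itself warns that attribution needs particular care because transplant patients have so many expected toxicities. Whether an event is drug-related will therefore often be a matter of judgement, and the main protection for a contested judgement is that whoever makes it has no stake in the answer.

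The protocol claims that protection by calling the board independent, then gives one of four seats to the sponsor. In a dispute over a DLT the sponsor is one of the two parties. At stake is whether the DLT count and the MTD can be reported as having been settled by an independent body.

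**Working it through.** The point is mainly one of comparing passages. The arithmetic only shows how much a single classification can be worth.

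**Step 1. Composition.** Section 3.3.2 lists two oncologists, one other specialist and the sponsor's biostatistician: 2 + 1 + 1 = 4. One of the four members comes from the sponsor. Nothing in the protocol makes that seat non-voting, limits it to presenting data, or removes it from disputes.

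**Step 2. Where the board decides DLT status.**

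| Situation | Who decides | Sponsor's position |
|---|---|---|
| Investigator and sponsor agree (3.3.2) | The two jointly | Openly a decision-maker |
| Investigator and sponsor disagree (3.3.2) | The board | A party, with one member on the board |
| Two or more subjects with a DLT (3.3.3) | The board reviews drug-relatedness and the DLT criteria | One member on the board |

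The third row means that the board can also revisit DLTs that were never disputed.

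**Step 3. Reproduce the plan's own figure.** Table 2 gives the probability of at most 1 DLT in 6. With independent subjects and true DLT rate p:

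P(X ≤ 1) = (1 − p)^6 + 6p(1 − p)^5

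- p = 0.10: 0.5314 + 0.3543 = 0.8857
- p = 0.20: 0.2621 + 0.3932 = 0.6554 (from unrounded terms)
- p = 0.30: 0.1176 + 0.3025 = 0.4202 (from unrounded terms)

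These match Table 2, as do the other five entries.

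**Step 4. How often could one reclassification move the count from above the limit to within it?** Only when the group has exactly 2 subjects with a true DLT:

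P(X = 2) = 15p²(1 − p)^4

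- p = 0.10: 15 × 0.01 × 0.6561 = 0.098
- p = 0.20: 15 × 0.04 × 0.4096 = 0.246
- p = 0.30: 15 × 0.09 × 0.2401 = 0.324

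If every such group had one true DLT classified as not a DLT, the Table 2 entry at 20% would rise from 0.6554 to 0.6554 + 0.2458 = 0.9011 (unrounded terms), and at 30% from 0.4202 to 0.4202 + 0.3241 = 0.7443. That is the extreme case, not a forecast.

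**Step 5. What these figures leave out.** For the count to be biased in this way, at least one of the two events must be in dispute or be re-reviewed, and the sponsor's member must sway the outcome. For escalation to follow, the investigators must also agree to it and the board must have no safety concern. The documents give no basis for estimating any of these, so Step 4 is an upper bound. It applies to a group of six, not to one expanded to 12 after a graft failure.

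**The case against.** The strongest case against is that the protocol contains real safeguards and that the decisive rules may lie in a document not shown. The Charter may make the seat non-voting or require recusal. One seat of four is a minority. A subject with a disputed DLT stops study drug while the board decides. The investigators, who are told of all reported toxicities, can withhold agreement to escalate even after losing a dispute, and the board can object on safety grounds whatever the count. The sponsor already confirms undisputed DLTs jointly with the investigator, so its role in classification is not hidden.

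Much of this stands, and it rules out several stronger readings that a reader might draw:

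- *That the sponsor holds a quarter of the votes, or that the board can deadlock 2–2.* The protocol does not say how the board votes. Voting and tie rules are properly left to the Charter, and their absence here is not a fault.
- *That the sponsor is on both sides of the dispute.* It is one party and has one seat on the deciding body. It is not on the investigator's side.
- *That one reclassified event decides escalation.* At most one DLT is necessary for escalation but not sufficient.
- *That 9.8% to 32.4% is the chance of a wrong escalation.* It is only the chance of exactly 2 DLTs in 6.

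What does not stand is that these safeguards restore independence. The investigators' veto applies to escalation, not to the DLT count. It does nothing for dose group 5, after which there is no further group but where the count still determines whether the MTD was exceeded. A recusal rule in the Charter would still leave the protocol's own sentence to be reconciled.

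**Conclusion.** The point holds in a limited form. The protocol claims independence for a board that, by its own description, includes a member from the sponsor, and it gives that board disputed DLT classifications and the re-review of drug-relatedness. The claim is therefore not met for the DLT count or the MTD.

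The size is one seat of four. A single classification could bring the count within the limit in at most 9.8%, 24.6% and 32.4% of six-subject groups at true DLT rates of 10%, 20% and 30%. The assumed rates are among those in Table 2, and subjects are taken as independent. The documents do not support a claim that DLT counts would in fact be biased, or by how much. The conclusion rests on the protocol text alone, with the Charter unseen. It is worth correcting before the study starts, but it does not invalidate the design.

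**What to change.** State in 3.3.2, and repeat in the Charter, that the sponsor's biostatistician is a non-voting member who prepares and presents data and takes no part in DLT adjudication or closed-session deliberation. If the Charter already says this, bring the protocol sentence into line with it.

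This costs one sentence in each document and needs no extra staff. No dose, threshold, sample size or Table 2 entry changes. Filling the seat with a statistician from outside the sponsor would also work, at most for a small fee. The change does not affect the joint confirmation of undisputed DLTs by investigator and sponsor, which the protocol states openly.
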